## MSSM Protocol Template HRP-503a

### Instructions:

1. Prepare a document with the following sections. Note that, depending on the nature of your research, certain sections below may not be applicable. Indicate N/A as appropriate, explaining where possible.
2. For any items described in the sponsor's protocol, grant application or other source documents submitted with the application, you may reference the title and page numbers of these documents rather than cutting and pasting into this document. **Do NOT refer to any derived documents, such as the Sample Consent document, or other internal documents required with the submission.**
3. If you reference page numbers, attach those pages to this protocol.
4. When you write a protocol, keep an electronic copy. You will need to modify this copy when making changes.

### 1) Objectives:

In this project we propose to conduct a 4-week open label cognitive enhancement trial of isradipine in up to 80 stable outpatients with schizophrenia and schizoaffective disorder.

The primary aim of this study is to evaluate the effects of the calcium channel antagonist, isradipine on cognitive dysfunction in patients with schizophrenia and schizoaffective disorder. Incomplete treatment response is common. Cognitive impairment and negative symptoms persist in a majority of patients even when positive psychotic symptoms are well-controlled, and they account for a large proportion of the variance in explaining functional disability (Keefe et al. 2007). This has led to a focused effort to target the specific treatment of cognition in patients with schizophrenia (Green and Nuechterlein, 2004), with somewhat limited success to date.

Novel treatment options have been limited by an incomplete understanding of the biological etiology of schizophrenia; however, recent data from the field of genomics have provided insights into the molecular underpinnings of schizophrenia and its associated symptoms. The majority of genetic risk loci identified to date show trans-disorder effects, increasing susceptibility across a broad range of neuropsychiatric disorders including schizophrenia and bipolar disorder (Williams et al. 2011; Purcell 2009). One possible explanation for this overlap is that several of these genes are influencing risk via their effects on shared phenotypes such as neurocognitive dysfunction. One such example is a single nucleotide polymorphism (SNP; rs1006737) in the calcium channel gene, CACNA1C; initially associated with bipolar illness (Sklar et al. 2008; 2011; Ferreira et al 2008) but also linked with schizophrenia (Green et al. 2009; Nyegaard et al. 2010) and recurrent major depression (Green et al, 2009). The strength of

	Protocol Title:	A Molecular Approach to Treat Cognition in Schizophrenia: Ca 2+ Channel Blockade
	Principal Investigator Name/Contact Info:	[name] [contact]
	Primary Contact Name/Contact Info:	[name] [REDACTED]
	Date Revised:	May 16, 2017
	Study Number:	HSM# 12-0031, GCO# 12-0679, GCO# 13-1987

the association signal for CACNA1C in major mental illness is unambiguous and several subsequent studies have evaluated the effects of CACNA1C variation on neurocognitive capacity.

## 2) Background

CACNA1C rs1006737 has been shown to affect neural networks underlying reward and emotional processing (Bigos et al. 2010; Wessa et al. 2010), verbal fluency (Krug et al. 2010), alerting and orienting aspects of attention (Thimm et al. 2011), and executive functions (Bigos et al. 2010). CACNA1C is responsible for coding the L-type voltage-gated calcium channel Cav1.2, which has been shown to be involved in synaptic plasticity, learning and memory in an NMDA-independent manner (Woodside et al. 2004; Moosmang et al. 2005; White et al. 2008) and CACNA1C knock-out mice show notable deficits in long term potentiation (Striessnig et al. 2006). These convergent data suggest that variation within CACNA1C may play a critical role in the development of neurocognitive deficits associated with schizophrenia and may point toward a novel treatment strategy targeting calcium channel dysfunction for these disabling symptoms.

Dysregulation of intracellular Ca2+ homeostasis and excess calcium signaling have been hypothesized to underlie multiple pathogenic processes in schizophrenia, including dopaminergic hyperactivity and hypofunction of the N-methyl-D-aspartate (NMDA) receptor (Bojarki et al. 2010). In selecting an intervention, we considered the numerous calcium-channel blockers that are widely utilized as anti-hypertensives; however, we chose isradipine for its specificity for the CaV1.2 channel subtype and its superior blood-brain barrier penetration.

## 3) Setting of the Human Research

The Icahn School of Medicine at Mount Sinai (ISMMS) site has ideal facilities for the proposed study. The research activities will be conducted in the Laboratory of Neurocognition located at [name]. This space, completely renovated in 2014, consists of a seven-room suite with ample space for research staff, interview rooms, and an exam room.

## 4) Resources Available to Conduct the Human Research

The current study will be performed in the Department of Psychiatry, located at the Icahn School of Medicine at Mount Sinai (ISMMS). Referrals will primarily come from Manhattan based Mount Sinai Health System Outpatient Psychiatry Departments. These will include the Mount Sinai Hospital, Beth Israel, and St. Luke's Roosevelt.

	Protocol Title:	A Molecular Approach to Treat Cognition in Schizophrenia: Ca 2+ Channel Blockade
	Principal Investigator Name/Contact Info:	[name] [contact]
	Primary Contact Name/Contact Info:	[name] [REDACTED]
	Date Revised:	May 16, 2017
	Study Number:	HSM# 12-0031, GCO# 12-0679, GCO# 13-1987

## 5) Study Design

### a) Recruitment Methods

Subjects will be recruited from the outpatient clinical services of the Mount Sinai Health System as described above. Potentially eligible patients are identified by the patient's clinical care provider (nurse practitioner and/or physician), who would then ask the patient's permission for our research team to approach and explain the protocol. A research team member will approach that individual and explain the study objectives, procedures, risks and benefits, and begin the informed consent process if the patient wishes to. We will also utilize IRB approved community based advertisements.

### b) Inclusion and Exclusion Criteria

**Inclusion criteria:** **1.** Age 18-60; **2.** DSM-IV schizophrenia or schizoaffective diagnosis; **3.** Residual phase of illness criteria met at screen and baseline as defined by item scores of  $\leq 4$  on each of the Brief Psychiatric Rating Scale (BPRS) hallucinatory behavior, unusual thought content, and conceptual disorganization items; **4.** Hamilton Rating Scale for Depression (HRSD)  $\leq 12$ ; **5.** Baseline Clinician Administered Ratings Scale for Mania (CARS-M) score of  $< 5$ ; **6.** Simpson Angus Scale (SAS) total score of  $\leq 6$ ; **7.** Treatment with at least one but no more than two stably-dosed second-generation antipsychotic medication (other than clozapine) for  $\geq 2$  months and no changes planned over the 4-week study period. First generation antipsychotics and clozapine are thought to cause significant cognitive impairment. Initial baseline cognitive functioning will not be evaluated as inclusion/exclusion criterion because schizophrenia/schizoaffective disorder have a relatively cognitively homogeneous patient sample. We do not anticipate any subjects without cognitive impairment. We will cover for baseline performance to determine if degree of cognitive impairment at baseline is responsible for any change noted.

**Exclusion criteria:** **1.** History of CNS trauma, neurological disorder, ADHD, mental retardation, learning disability, or other non-schizophrenic cause of cognitive impairment; **2.** DSM-IV diagnosis of substance abuse/dependence within 3 months or positive urine toxicology at screening that is not consistent with what participant reported. Substance abuse and dependence are determined based on an extremely comprehensive interview (the SCID), which evaluates lifetime history and current history of all substance use disorders. As per the protocol, DSM-IV diagnosis of substance abuse or dependence within 3 months will be exclusionary (not substance use); **3.** Pregnant women or women of child bearing potential who are not using a medically accepted means of contraception (including oral contraceptive or implant, condom, diaphragm, spermicide, intrauterine device, tubal ligation, or partner with vasectomy) **4.** Women who are breastfeeding; **5.** Active, unstable medical problem that may interfere with cognition; **6.** Current treatment for hypertension; **7.** Uncontrolled hypertension; **8.** History of heart

	Protocol Title:	A Molecular Approach to Treat Cognition in Schizophrenia: Ca 2+ Channel Blockade
	Principal Investigator Name/Contact Info:	[name] [contact]
	Primary Contact Name/Contact Info:	[name] [REDACTED]
	Date Revised:	May 16, 2017
	Study Number:	HSM# 12-0031, GCO# 12-0679, GCO# 13-1987

disease; **9.** Any drug known to interact with isradipine. **10.** History of GI strictures; **11.** Abnormal lab or ECG at screen. **12.** Significant suicidal ideation at baseline (HRSD item 3 > 2). Concomitant Medications: Practical and ethical considerations prevent an exclusive focus on medication-free patients; however, we will limit participation to individuals taking at least one and no more than 2 concomitant antipsychotic medications and we will exclude subjects who have received ECT within 12 months. Medication load will be incorporated as covariates in statistical analyses using chlorpromazine (CPZ) equivalents.

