### c) Number of Subjects

Up to 80 stable schizophrenia and schizoaffective patients will be recruited from the Mount Sinai Health System Outpatient Departments, and community advertisements.

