### e) Study Endpoints

The primary endpoint related to the efficacy of isradipine will be cognitive enhancement measured by the MATRICS Consensus Cognitive Battery (MCCB). The MCCB is accepted by the FDA as a primary outcome measure for registry trials of cognitive enhancement in schizophrenia.

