### f) Procedures Involved in the Human Research

All eligible subjects will undergo visits at screening, baseline (week 0), visit 8 hours after week 0, week 1, week 2, visit 8 hours after week 2, week 3, and week 4 (end of study). The parameters of study drug dosing are as follows: isradipine as utilized in this trial will be administered twice daily. Isradipine will be titrated as follows: baseline (week 0) 5 mg/day BID; Week 2 increase to 10 mg/day BID if 5 mg was well-tolerated. Dosing will be flexible based on side effects with a maximum=10 mg/day. If 5 mg cannot be tolerated, the subject will be discontinued. Dosing was based on package labeling for hypertension and prior studies in Parkinson's disease (Simuni et al. 2010).

	Protocol Title:	A Molecular Approach to Treat Cognition in Schizophrenia: Ca 2+ Channel Blockade
	Principal Investigator Name/Contact Info:	[name] [contact]
	Primary Contact Name/Contact Info:	[name] [REDACTED]
	Date Revised:	May 16, 2017
	Study Number:	HSM# 12-0031, GCO# 12-0679, GCO# 13-1987

Measures described in detail below:

Safety Outcome Measures

- The Side Effects Checklist (SEC; physician administered) and side effect self-report form – (all visits)
- Vital signs including blood pressure (standing/supine – all visits)
- Blood pressure check within 8 hours of first dose. Staff contact number will be given to subject in case there are any problems before the 8 hour BP check (week 0). An additional blood pressure check 8 hours after increased dosage (week 2).
- Electrocardiogram (ECG); chemistry panel and CBC via blood draw (approximately 2 TSP blood drawn); urinalysis (screening & week 4)
- Urine toxicology (screening)
- Urine pregnancy test for women of childbearing potential (baseline)
- Abnormal Involuntary Movement Scale (AIMS) and Simpson Angus Scale (SAS) (all visits)
- Beck Scale for Suicidal Ideation (SSI) and Columbia Suicide Severity Rating Scale (C-SSRS) (all visits)

Clinical/Symptom Measures

- Structured Clinical Interview for the DSM-IV (SCID-IV) (screening)
- Symptom rating scales including the Brief Psychiatric Rating Scale (BPRS), the Scale for the Assessment of Negative Symptoms (SANS), the Hamilton Rating Scale for Depression (HRSD), the Clinical Global Impression Scale (CGI), the Clinician Administered Rating Scale for Mania (CARS-M) (all visits)

Neurocognitive/Functional Measures

- MATRICS Consensus Cognitive Battery\* (baseline & week 4)

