Data from this study may be used in medical publications or presentations. The information will be de-identified so that individual subjects cannot be recognized and the information will no longer be considered PHI. The information that is collected for research will be analyzed for many years and it is not possible to know how long this analysis and follow-up will take. Therefore, participants are allowing access to this information indefinitely.

Subjects will only be identified with a numerical code in compliance with HIPAA regulations. Raw subject data will be secured in double locked physical control. Digitized raw data will be similarly de-identified using coding and will be secured on an MS SQL server with Windows integrated security.

	Protocol Title:	A Molecular Approach to Treat Cognition in Schizophrenia: Ca 2+ Channel Blockade
	Principal Investigator Name/Contact Info:	[name] [contact]
	Primary Contact Name/Contact Info	[name] [REDACTED]
	Date Revised:	May 16, 2017
	Study Number:	HSM# 12-0031, GCO# 12-0679, GCO# 13-1987

Data analysis plan is included below. All analyses will be based on an intent-to-treat sample of subjects who received at least one dose of isradipine. Since the missing values may be dependent on the observed outcomes, we assume the missing data mechanism to be missing at random, and hence a mixed models analysis will be used to assess the treatment effect of isradipine with fixed effects for week and first order autoregressive covariance structure to evaluate change over time for all of the primary outcome measures. Cognitive measures will be handled differently, as these will only be collected at two time points – if missing data are substantial (or a complete visit is missing), subjects' data will not/cannot be meaningfully analyzed.

*Primary Analyses* will test the following hypotheses based on our specific aims:

To determine the feasibility of 4 weeks of isradipine on cognitive outcomes in SZ.  
Hypothesis: We will successfully recruit up to 80 stable schizophrenia and schizoaffective patients

To determine the safety of 4 weeks of isradipine on cognitive outcomes in SZ.  
Hypothesis: The frequency of new or worsened side effects (clinician-rated; self-reported; lab-based) will not be significantly different from baseline to end of study visit.

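### In one arm with a single pre-treatment MCCB, the slope of change on baseline cannot show that baseline impairment explains the change: measurement error alone gives an expected slope of -(1-r)

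*Combined protocol and SAP*

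**What the plan says.** Section 1 (Objectives) describes a "4-week open label cognitive enhancement trial of isradipine in up to 80 stable outpatients". There is no control group. Section 5e makes the MCCB the primary efficacy endpoint, and section 5f schedules the "MATRICS Consensus Cognitive Battery" at baseline and week 4 only.

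The use of baseline cognition is described in section 5b, within the eligibility criteria. No cognitive threshold applies at entry: "Initial baseline cognitive functioning will not be evaluated as inclusion/exclusion criterion". The reason given is that "schizophrenia/schizoaffective disorder have a relatively cognitively homogeneous patient sample". The text then says: "We will cover for baseline performance to determine if degree of cognitive impairment at baseline is responsible for any change noted". The verb is presumably meant to be covary.

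The analysis text in section 5h gives no model for this. It says "Cognitive measures will be handled differently, as these will only be collected at two time points", and that patients with substantial missing cognitive data or a missing visit will not be analysed. The documents contain no second pre-treatment MCCB, no reliability figure, and no allowance for regression to the mean.

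**The concern.** The stated purpose is to decide what is responsible for change, which goes beyond adjusting for precision. The baseline coefficient itself is to be interpreted. Change is week 4 minus baseline, so the measurement error in the baseline score sits in the predictor and, with opposite sign, in the outcome. A patient who scores low by chance at baseline will tend to appear to improve, and one who scores high by chance will tend to appear to decline.

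Taking higher scores as better, the expected result is that more impaired patients seem to gain more, whether or not isradipine does anything. With one arm there is no treatment-by-baseline interaction to test, and with one pre-treatment score the error cannot be estimated from the trial's own data.

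Section 8 says the results may form the basis for larger pivotal trials. A spurious dependence on baseline could lead such trials to recruit low scorers. Once patients are selected on a low score, regression to the mean does bias the mean change.

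**Working it through.** **Inputs from the documents.** One arm; two MCCB assessments; no selection on MCCB; up to 80 patients, which is a ceiling (section 5c). There is no planned figure to reproduce.

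**Assumptions.** Two-sided alpha 0.05; equal SD at both visits; r from 0.7 to 0.95; normal scores; n = 80 or 40 analysable. The documents state none of these apart from the ceiling of 80.

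**Algebra.** Let the baseline score be X = T + e1 and the week-4 score be Y = T + d + e2. The true change d is the same for everyone, Var(X) = s², Var(T) = r·s², and each error variance is (1-r)·s². Change is D = d + e2 - e1.

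- Cov(X, D) = -(1-r)·s², so the slope of D on X is -(1-r).
- Var(D) = 2(1-r)·s², so corr(X, D) = -(1-r)/sqrt(2(1-r)) = -sqrt((1-r)/2).
- The expected gap in change between the lower and upper halves by baseline is 2·sqrt(2/pi)·(1-r) = 1.596(1-r) baseline SDs.

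**Results.** Rejection rates come from at least 20,000 simulated trials per setting:

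| r | Slope | Correlation | Spurious half-to-half gap (SD) | Falsely significant, n = 80 | Falsely significant, n = 40 |
|---|---|---|---|---|---|
| 0.95 | -0.05 | -0.16 | 0.08 | 29% | 16% |
| 0.9 | -0.10 | -0.22 | 0.16 | 52% | 29% |
| 0.8 | -0.20 | -0.32 | 0.32 | 82% | 52% |
| 0.7 | -0.30 | -0.39 | 0.48 | 95% | 71% |

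**Hand check at r = 0.8, n = 80.** t is about -0.316·sqrt(78/(1-0.1)) = -2.94 against a critical value of 1.99. The rejection probability is about Phi(2.94-1.99) = Phi(0.95) = 0.83, in line with 82%.

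**When the artefact vanishes.** The slope is r·(SD at week 4/SD at baseline) - 1. It is zero in expectation only if r = 1 or if the week-4 SD exceeds the baseline SD by a factor of 1/r: 1.05, 1.11, 1.25 or 1.43 for the four values of r.

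**Mean change.** E(D) = d, because no one is admitted or excluded on X. With baseline centred at the sample mean, the fitted intercept equals the observed mean change.

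**Alternative analyses.** Oldham's method (change against the average of the two scores) rejected in about 5% of the same null trials. That depends on equal variances under the null. If true change varies between patients independently of baseline with SD 0.5 of the baseline SD, the week-4 variance becomes 1 + 0.25 = 1.25 times the baseline variance. Oldham's method then rejects in about 38%, 29% and 24% of trials at n = 80 for r = 0.9, 0.8 and 0.7, in the opposite direction. With SD 0.2 (variance ratio 1.04) it rejects in about 5 to 7%.

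A reliability-corrected slope is (b + 1 - r)/r, where b is the observed slope. For an illustrative b = -0.20 it is -0.10/0.9 = -0.11 at r = 0.9, 0 at r = 0.8, and 0.10/0.7 = +0.14 at r = 0.7. The sign depends on r, so a range has to be shown.

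**The case against.** **The model is not written down.** Section 5b has one loosely worded sentence and does not say whether the outcome is change or the week-4 score. That is true, but the purpose is stated, and no usual model rescues it. If the outcome is the week-4 score, the baseline coefficient has expectation r, which is again non-zero whatever the drug does.

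**The sentence may describe a check on a rival explanation.** On this reading the investigators would ask whether change reflects starting level and not the drug, and a negative slope would make them more cautious. The reading is fair, but the inference is still wrong: the slope would usually point to baseline as the explanation when there is only measurement error, and a real mean change could be discounted.

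**The error rates rest on assumed reliability and sample size.** This stands. At r = 0.95 and n = 40 the rate is 16%, and practice gains that were larger in better performers could offset part of the slope. The documents give no data on either. The protocol's own description of a cognitively homogeneous sample points towards a lower r in this sample, and so a larger artefact.

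**A reader might infer that the test of mean change is also corrupted**, for example if baseline were entered uncentred and the intercept read as the change. The documents do not support that: nothing says baseline would be uncentred or that an intercept would be tested.

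**This is a side question.** It is neither the MCCB endpoint itself nor one of the hypotheses listed under Primary Analyses in section 5h. That limits its weight. It remains an explicitly planned inference.

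**Conclusion.** The concern holds for interpretation of the baseline slope. Under equal SDs and no true link between impairment and change, the expected slope is -(1-r). At n = 80 the false-positive rate runs from about 29% (r = 0.95) to 95% (r = 0.7), against a nominal 5%. The negative expected slope does not require identical true change in every patient, only change unrelated to baseline.

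Two stronger readings should be resisted. The trial is not certain to report such a finding; this is a bias in expectation, and significance depends on r and the number analysed. Nor does the artefact create a false mean improvement, since there is no selection on the MCCB. Practice effects and the lack of a control arm do threaten the reading of mean change, but that is a separate matter.

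**What to change.** Add two statements to the analysis text in section 5h and amend the sentence in section 5b to match:

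1. The cognitive effect is the mean MCCB change from baseline to week 4 with its 95% CI. If baseline is a covariate, it is centred at the sample mean.
2. The slope of change on baseline will not be read as baseline impairment explaining the change.

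If the baseline question is kept, label it exploratory. Either relate change to the average of the baseline and week-4 scores (Oldham's method; Pitman's comparison of the two variances is the same test, so one is enough), or report the reliability-corrected slope over a stated range of r.

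The cost is a few sentences and at most one extra analysis of data already collected. The downside is small but should be stated: Oldham's method can show a false association in the opposite direction if true change varies between patients, the corrected slope depends on the r assumed, and neither separates a drug effect from a practice effect without a control arm.

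### The medication-stability rule and the medication covariate cover antipsychotics only, so changes in other psychotropic or anticholinergic drugs can bias the MCCB change in either direction

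*Combined protocol and SAP*

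**What the plan says.** The Objectives (section 1) describe the population as "stable outpatients with schizophrenia and schizoaffective disorder". In section 5b, medication stability is made operational only in inclusion criterion 7: "Treatment with at least one but no more than two stably-dosed second-generation antipsychotic medication (other than clozapine) for" at least 2 months, with "no changes planned over the 4-week study period".

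The Concomitant Medications text at the end of section 5b adds three things:
- a limit on the number of antipsychotics: "we will limit participation to individuals taking at least one and no more than 2 concomitant antipsychotic medications";
- an ECT window: "we will exclude subjects who have received ECT within 12 months";
- an adjustment: "Medication load will be incorporated as covariates in statistical analyses using chlorpromazine (CPZ) equivalents".

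The remaining drug-related limits are the exclusions for current antihypertensive treatment and for "Any drug known to interact with isradipine". Neither concerns how recently a drug was changed or whether it affects cognition.

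The trial is open label with a single arm (section 1). The primary efficacy endpoint is the MCCB (section 5e), given at baseline and week 4 (section 5f). The measures listed in section 5f include no concomitant-medication log. The analysis text in section 5h says that cognitive measures are treated separately because they have two time points, and then deals only with missing data.

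**The concern.** The protocol already treats drug effects on cognition as a threat. It bars clozapine and first-generation antipsychotics because it regards them as cognitively impairing, and it excludes recent ECT. Yet it requires stability for one drug class only. Schizoaffective disorder is eligible, so antidepressants and mood stabilisers are foreseeable, as are sedatives and anticholinergics in either diagnosis.

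A patient who stopped a sedating drug days before baseline can meet every listed criterion. If cognition then recovers over the next four weeks, the gain appears in the MCCB change. Starting such a drug would hide a real benefit. With no control arm to share these background changes, and no assessment between baseline and week 4, the data cannot separate them from isradipine. Chlorpromazine equivalents express antipsychotic dose, so this covariate carries no information about the other drugs.

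**Working it through.** **1. What the text covers.**

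| Provision | Antipsychotics | Other psychotropics and anticholinergics |
|---|---|---|
| Stable for at least 2 months before entry (5b, inclusion 7) | Yes | No |
| No change planned for 4 weeks (5b, inclusion 7) | Yes | Not on the natural reading |
| Limit on number of drugs (5b) | Yes | No |
| Covariate (5b, CPZ equivalents) | Yes | No |
| Log of changes (5f) | None listed | None listed |
| Analysis rule after a change (5h) | None | None |

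**2. Size.** The plan states no alpha, MCCB test, power, standard deviation or rate of medication change, so it has no figure to reproduce. What follows is an illustration, and every input except the ceiling of 80 is assumed:
- two-sided 5% paired test of mean MCCB change, with no true isradipine effect and no practice effect;
- retest correlation *r* of 0.8 to 0.9;
- a fraction *f* of 10% or 20% of patients with a change in another drug;
- a net shift *d* of 0.3 SD in one direction among those patients;
- *n* = 80 completers (the recruitment ceiling) or 40.

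Formulas, in units of the MCCB SD:
- bias in the mean = *f* × *d*, which is 0.10 × 0.3 = 0.03 or 0.20 × 0.3 = 0.06;
- SE of the mean change = √(2(1 − *r*)/*n*);
- rejection rate = 1 − Φ(1.96 − bias/SE) + Φ(−1.96 − bias/SE).

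| *n* | *r* | SE | Bias 0.03: bias/SE, rejection | Bias 0.06: bias/SE, rejection |
|---|---|---|---|---|
| 80 | 0.8 | 0.0707 | 0.42, 7.1% | 0.85, 13.6% |
| 80 | 0.9 | 0.0500 | 0.60, 9.2% | 1.20, 22.4% |
| 40 | 0.8 | 0.1000 | 0.30, 6.0% | 0.60, 9.2% |
| 40 | 0.9 | 0.0707 | 0.42, 7.1% | 0.85, 13.6% |

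The range is about 7% to 22% with 80 completers and 6% to 14% with 40. Adding the between-patient variance that the shift itself creates, *f*(1 − *f*)*d*², lowers the largest value only from 22.4% to 21.3%.

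**3. If shifts go both ways.** When gains and losses balance, the bias is zero and the rate stays near 5%. The changes then add noise only.

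**The case against.** The strongest case is that the plan is less open than its wording on stability suggests. BPRS item ceilings at both screen and baseline, with ceilings on the HRSD, CARS-M and SAS, keep out many patients whose symptoms would prompt a change in mood or side-effect medication. Drugs that interact with isradipine are excluded. Section 5j discontinues patients who worsen, and section 5h does not analyse cognitive data when a complete visit is missing. All of this stands and should make such changes rarer. But these provisions measure symptoms or interactions. A patient can satisfy them soon after a drug change, and withdrawal on worsening does not catch the patient who improves after stopping an impairing drug.

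The no-planned-change phrase names no drug, so it could be read to cover all medication. Its place in the antipsychotic criterion makes that the less natural reading, and even so it would give other drugs no window before baseline.

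It is also fair that the error rates belong to a test the plan does not specify, that the primary hypotheses listed in section 5h are feasibility and safety, and that 80 is a ceiling. Practice and time effects of a single arm tested twice reach every patient and are probably the larger limitation. That makes this a secondary source of bias, but one that can be reduced without adding an arm.

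A reader might infer more: that the protocol declares patients eligible although another drug is changed during the trial, or that the reported gain will in fact be a medication artefact. The documents support neither. Eligibility is settled at entry; for later changes, the accurate statement is that the plan does not restrict, schedule the recording of, or analyse them. Nothing in the documents shows how common such changes are or which way they point.

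**Conclusion.** The gap is real and follows from the text: the stability window and the medication covariate both concern antipsychotics only, and the existing safeguards narrow the exposure without closing it. The MCCB change can be biased upward or downward as a result.

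The size cannot be established from the documents. The inflation calculated above needs changes that are fairly common and mostly in one direction, and the plan gives no evidence for either condition. The point therefore supports a modest, inexpensive correction. It does not support a claim that the trial's result is invalid.

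**What to change.** 1. Extend the stability clause of inclusion 7, with its 2-month window and no planned change through week 4, to all concomitant psychotropic and anticholinergic drugs.
2. Record concomitant medication at the existing visits: drug, dose, and date of any start, stop or change.
3. Prespecify a sensitivity analysis of MCCB change that excludes or flags patients with a change. Label it supportive only: it conditions on an event after baseline that treatment may influence, so it can introduce selection bias of its own.

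How medication changes during the trial relate to the discontinuation rules in section 5j is for the investigators to reconcile. This review proposes no rule on it.

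The cost is a short eligibility amendment, a brief log that section 5f does not now list, and deferral of some patients until they are stable. The document is dated May 2017 and gives an anticipated final date of 7/2017, so the eligibility change may reach few patients. The log and the sensitivity analysis could still serve patients already enrolled, as far as their medication can be reconstructed from records. Practice and time effects of the single-arm design would remain after all three changes.
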